9.3.3.3 Criteria for Termination of the Study (Holding Rules)

Safety holding rules will apply throughout the entire study period. Further injections will be discussed with the Local Safety Board. Should a holding rule be activated, the PI will inform the sponsor. The sponsor has to inform the competent authorities and the ethics committee within 15 days.

If the event(s) occur in the higher-dose cohort, the follow-up phase of the lower dose cohort will continue. The discontinuation of a holding rule should be communicated to all entities in the same manner and timeframe as described above.

The Local Safety Board review will consider:

- The relationship of the AE or SAE to the vaccine
- The relationship of the AE or SAE to the vaccine dose, or other possible causes of the event
- If appropriate, additional screening or laboratory testing for other subjects to identify those who may develop similar symptoms, and alterations to the current informed consent form will be discussed

All injected subjects will be followed for safety until resolution or stabilization (if determined to be chronic sequelae) of their AE. AE grading will be done according to FDA's 2007 voluntary guidance: (14) or according to CTCAE v4 (15). Please refer to Table 3- Table 5 for further details.

The holding rules are as follow:

- Solicited (expected) local adverse events:
 - If more than 25% of injections (minimum 2 individuals) are followed by Grade 3 solicited swelling or pain or Grade 4 redness beginning within 3 days after injection (day of injection and one subsequent day) and persisting at Grade 3 (swelling or pain)/4 (redness) for >48 – 72 hours
- Solicited (expected) systemic adverse events:
 - If more than 25% of injections (minimum 2 individuals) are followed by Grade 3 solicited systemic AE (or Grade ≥ 3 physical observations as defined above and in Section 9.7.11) beginning within 3 days after study injection (day of injection and one subsequent day) and persisting at Grade ≥ 3 for >48 – 72 hours
- Unsolicited (unexpected) adverse events:
 - If more than 25% of subjects (minimum of 2 individuals) develop a Grade ≥ 3 unsolicited AE (including laboratory AE and physical observations) that is considered probably or definitely related to injection and persists at Grade 3 for >48 – 72 hours
- A serious adverse event occurs that may be related to the IMP

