9.7.7.2 Serious Adverse Event Definition

A Serious Adverse Event (SAE) is any untoward medical occurrence (whether considered to be related to investigational medicinal product or not) that at any dose:

- Results in death
- Is life-threatening
- Requires inpatient hospitalization or prolongation of existing hospitalization
- Results in persistent or significant disability/incapacity
- Is a congenital abnormality/birth defect
- Is an Important Medical Event, i.e., an event that may jeopardize the subject and may require medical or surgical intervention to prevent one of the outcomes listed in this definition.

Hospitalizations which are the result of elective or previously scheduled surgery for pre-existing conditions which have not worsened after initiation of treatment should not be classed as SAEs. For example, an admission for a previously scheduled ventral hernia repair would not be classed as an SAE.

However, complication(s) resulting from a hospitalization for an elective or previously scheduled surgery that meets serious criteria must be reported as an SAE(s).

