9.7.11 Assessment of Severity

The severity of clinical and laboratory AE will be assessed according to the following scales.

9.7.11.1 Toxicity Grading Scale for Local Adverse Events**Table 3: Toxicity grading scale for local adverse events**

Local Reaction	Grade 0 Normal	Grade 1 Mild	Grade 2 Moderate	Grade 3 Severe	Grade 4 Potentially life-threatening
Redness/erythema*	<25 mm	25-50 mm	51-100 mm	>100 mm	Necrosis or exfoliative dermatitis
Swelling/induration**	<25 mm	25-50 mm and does not interfere with activity	>50 mm or interferes with activity	Prevents daily activity	Necrosis
Pain	None	Does not interfere with activity	Interferes with activity	Prevents daily activity	Emergency room visit or hospitalization

*In addition to grading the measured local reaction at the greatest single diameter, the measurement should be recorded as a continuous variable.

**Induration/swelling should be evaluated and graded using the functional scale as well as the actual measurement.

From the FDA's 2007 voluntary guidance: (<http://www.fda.gov/downloads/BiologicsBloodVaccines/GuidanceComplianceRegulatoryInformation/Guidances/Vaccines/ucm091977.pdf>)

9.7.11.2 Toxicity Grading Scale for Physical Observations**Table 4: Toxicity grading scale for physical observations**

Observation	Grade 1	Grade 2	Grade 3	Grade 4	Grade 5
Fever (axillary)	38.0° - 39.0°C	> 39.0°C - 40.0°C	> 40.0°C for ≤ 24 hours	> 40.0°C for ≥ 24 hours	Death
Tachycardia (bpm)*	Asymptomatic, intervention not indicated	Symptomatic, non-urgent medical intervention indicated	Urgent medical intervention indicated	Life-threatening consequences, urgent intervention indicated	Death
Bradycardia (bpm)**	Asymptomatic, intervention not indicated	Symptomatic, medical intervention indicated	Severe, medically significant, urgent medical intervention indicated	Life-threatening consequences, urgent intervention indicated	Death

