9.7.11.3 Toxicity grading scale for systemic AEs excluding the physical observations listed above

Table 5: Toxicity grading scale for systemic AEs

Systemic sign/symptom	Grade 1 Mild	Grade 2 Moderate	Grade 3 Severe	Grade 4 Potentially life-threatening
Headache	No interference with activity	Some interference with activity	Significant; prevents daily activity	Medical consultation and/or hospitalization
Fatigue	No interference with activity	Some interference with activity	Significant; prevents daily activity	Medical consultation or hospitalization
Myalgia	No interference with activity	Some interference with activity	Significant; prevents daily activity	Medical consultation and/or hospitalization
Arthralgia	No interference with activity	Some interference with activity	Significant; prevents daily activity	Medical consultation and/or hospitalization
Chills	No interference with activity	Some interference with activity	Significant; prevents daily activity	Medical consultation and/or hospitalization
Sweats	No interference with activity	Some interference with activity	Significant; prevents daily activity	Medical consultation and/or hospitalization
Subjective Fever	No interference with activity	Some interference with activity	Significant; prevents daily activity	Medical consultation and/or hospitalization
Nausea	No interference with activity	Some interference with activity not requiring medical intervention	Prevents daily activity and requires medical intervention	Medical consultation and/or hospitalization
Vomiting	No interference with activity	Some interference with activity not requiring medical intervention	Prevents daily activity and requires medical intervention	Medical consultation and/or hospitalization
Abdominal Pain	No interference with activity	Some interference with activity not requiring medical intervention	Prevents daily activity and requires medical intervention	Medical consultation and/or hospitalization
Diarrhea	No interference with activity	Some interference with activity not requiring medical intervention	Prevents daily activity and requires medical intervention	Medical consultation and/or hospitalization
Other systemic symptoms	No interference with activity	Some interference with activity	Prevents daily activity	Medical consultation and/or hospitalization

From the FDA's 2007 voluntary guidance: (<http://www.fda.gov/downloads/BiologicsBloodVaccines/GuidanceComplianceRegulatoryInformation/Guidances/Vaccines/ucm091977.pdf>)

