9.10 Local Safety Board

During the trial, the Local Safety Board will review and judge the safety, tolerability, after each dose-step and prior to the next dose-step of the trial. Based on these data the Local Safety Board will/may decide

- Whether there will be a next dose cohort and if the planned dose for the next dose cohort has to be reduced.
- Whether there will be added additional dose step(s) or dose step(s) will be repeated.

Evaluation will take the results of the pre-clinical studies and the ongoing phase I studies in prior mentioned other countries into account.

An interim safety report, summarizing the safety (AEs, vital signs, 12-lead ECGs, and laboratory safety data) will be prepared and reviewed by the Principal Investigator and Medical Monitor before the second immunization for each dose cohort.

Planned dose escalation will occur after the second immunization of all subjects of the 1st dose group following a review of the interim safety report summarizing the safety (AEs, vital signs, 12-lead ECGs, and laboratory safety data) and any available immunological data by the Principal Investigator and Medical Monitor.

The dose for the next escalation step may be reduced if there are concerns about the safety. A dose level may be repeated and furthermore, additional dose step(s) may be added but not exceeding dose of 1×10^8 pfu MVA-MERS. The decision to repeat and/or to modify the dose level and/or to add additional dose steps will be taken by the Local Safety Board.

In addition, a Local Safety Board meeting will be conducted whenever safety relevant data occur that might have an influence on the trial.

Members of the Local Safety Board will be the medical monitor, as well as the Principal Investigator, or at least one of the deputies and a representative of the sponsor.

At a minimum the holding rules (criteria for termination of the study) specified in the protocol will automatically apply (if activated) for not proceeding with a higher dose.

The decisions of the Local Safety Board meeting will be briefly summarized by CTC North and signed by all members involved in the meeting and the decision. The summarized safety report of each Local Safety Board Meeting will be submitted to the competent national authority (Paul-Ehrlich-Institute) and the independent ethics committee (Ethik-Kommission der Ärztekammer Hamburg) for notification.

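### The percentage holding rules use Grade 3 and Grade ≥ 3 inconsistently, so read literally a non-serious Grade 4 event can go uncounted where a Grade 3 event would count

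*Protocol*

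**What the plan says.** Protocol 9.3.3.3 lists four holding rules. Three are percentage rules, each needing more than 25% (of injections for the two solicited rules, of subjects for the unsolicited rule) and at least two individuals. Each has an entry grade and a grade at which the event must persist for more than 48–72 hours.

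- **Local:** swelling or pain enters at Grade 3 and redness at Grade 4. The event must be "persisting at Grade 3 (swelling or pain)/4 (redness").
- **Systemic:** the rule counts injections that "are followed by Grade 3 solicited systemic AE". In the same sentence physical observations enter at Grade ≥ 3, and persistence is at Grade ≥ 3.
- **Unsolicited:** entry is at Grade ≥ 3, but the event must be one that is "considered probably or definitely related to injection and persists at Grade 3".

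The fourth rule has no percentage: "A serious adverse event occurs that may be related to the IMP".

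Section 9.10 states that the holding rules "will automatically apply (if activated) for not proceeding with a higher dose", and presents this as a minimum.

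**The concern.** A holding rule should become easier to meet as reactions become more severe. Here the lower bound is written as Grade ≥ 3 in some clauses and plain Grade 3 in others, and nothing in the protocol says that plain Grade 3 means Grade 3 or higher. Because the sign is used in neighbouring clauses, and because the local rule separates Grade 3 from Grade 4, a literal reader cannot assume it.

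In a first-in-human dose escalation these rules are the part of the safety decision that does not depend on judgement. If a Grade 4 event replaces a Grade 3 event, the automatic bar to the higher dose can change from met to not met. The notice to the authorities and the ethics committee within 15 days (9.3.3.3) also depends on a rule being activated.

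**Working it through.** **Step 1. Entry and persistence clauses side by side (9.3.3.3).**

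| Rule | Entry grade | Persistence grade | Grade 4 event, read literally |
|---|---|---|---|
| Local, swelling or pain | 3 | 3 | not counted |
| Local, redness | 4 | 4 | counted |
| Systemic, solicited symptom | 3 | ≥ 3 | not counted if Grade 4 from the start; arguably counted if it worsens from 3 to 4 |
| Systemic, physical observation | ≥ 3 | ≥ 3 | counted |
| Unsolicited | ≥ 3 | 3 | admitted at entry, fails persistence if it stays at Grade 4 |

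Each rule has at least one gap. Section 9.7.2 adds to the problem: a change in severity is captured as a new event. Pain that moves from Grade 3 to Grade 4 after a day then ends its Grade 3 record and may not reach the required duration.

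**Step 2. Does the serious-event rule close the gap?** The hospital criterion in 9.7.7.2 is "Requires inpatient hospitalization or prolongation of existing hospitalization". Grade 4 can be reached with less:

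- Table 3 defines Grade 4 pain as "Emergency room visit or hospitalization", so an emergency room visit without admission is enough.
- Table 5 defines Grade 4 fatigue as "Medical consultation or hospitalization", with near-identical wording for the other symptoms, so a consultation alone is enough.
- The unsolicited rule includes laboratory events, and a Grade 4 laboratory value need not be serious.

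These non-serious events are the ones left out.

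**Step 3. Counts needed.** The rule needs the smallest k with k/n > 0.25 and k ≥ 2. The protocol does not say whether the percentage is taken over one injection round or both, so both are shown for a cohort of 12.

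- n = 12: 3/12 = 25.0% is not more than 25%, so k = 4 (4/12 = 33.3%).
- n = 24: 6/24 = 25.0% is not more than 25%, so k = 7 (7/24 = 29.2%).

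The most severe patterns that still miss the local rule, with every Grade 4 event non-serious, are:

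- n = 12: 3 at Grade 3 plus 9 at Grade 4. All 12 are at Grade ≥ 3, and only 3 count.
- n = 24: 6 at Grade 3 plus 18 at Grade 4. All 24 are at Grade ≥ 3, and only 6 count.

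**Step 4. Chance that one rule is met.** The event rates are assumptions, because the protocol gives none, and injections are treated as independent. For n = 12,

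P(X ≥ 4) = 1 − Σ(x = 0 to 3) C(12, x) pˣ (1 − p)¹²⁻ˣ.

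With few reactions (5% persistent Grade 3, plus 1% to 5% persistent non-serious Grade 4):

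- Grade 4 left out, p = 0.05: 0.0022
- Grade 4 counted, p = 0.05 + 0.01 = 0.06: 0.0043
- Grade 4 counted, p = 0.05 + 0.05 = 0.10: 0.0256

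With many reactions (20% Grade 3, plus 5%, 10% or 20% non-serious Grade 4):

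| n (count needed) | Grade 4 left out | +5% counted | +10% counted | +20% counted |
|---|---|---|---|---|
| 12 (4) | 0.205 | 0.351 | 0.507 | 0.775 |
| 24 (7) | 0.189 | 0.393 | 0.611 | 0.904 |

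These are probabilities for a single percentage rule. They are not the trial's overall chance of a hold, which also includes the serious-event rule.

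**The case against.** The strongest reply is that this is untidy wording with an obvious meaning. A rule that admits Grade ≥ 3 cannot sensibly reject an event for staying at Grade 4, and a board reading the section as a whole would treat Grade 3 as a floor. The inconsistent use of the sign lies within the systemic and unsolicited rules, since the local rule never uses it.

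The affected class is also narrow. The serious-event definition includes important medical events, so Grade 4 swelling (necrosis) would probably trigger a hold anyway. Grade 4 pain and the Table 5 symptoms are defined by a contact with care, so persistence at Grade 4 for more than 48–72 hours needs repeated contacts or a grade carried forward. Nine such subjects out of 12, none serious, is not realistic.

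Finally, the percentage rules do not act alone. The Local Safety Board reviews each subject's data before the second injection and the interim report before escalation (9.4.1), and it meets whenever relevant safety data arise (9.10). Section 9.4.1 also foresees safety events that stop escalation without meeting a holding rule.

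Most of this stands as a limit on the practical effect. It does not repair the rule: Board review is discretionary, whereas section 9.10 makes the written threshold automatic, and the intended meaning has to be inferred because no clause states it.

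**Conclusion.** The concern holds. Read literally, all three percentage rules leave out some non-serious Grade 4 events that would count at Grade 3, and the threshold is not monotone in severity. Grade 4 redness, Grade 4 physical observations under the systemic rule, and possibly related serious events are covered.

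The size depends on how often persistent, non-serious Grade 4 events occur, which the protocol does not state. Where reactions are rare the difference is small in absolute terms. Where 20% of injections give a persistent Grade 3 reaction and another 10% a non-serious Grade 4 reaction, the chance of meeting a rule in 12 injections is 0.205 as written and 0.507 with Grade 4 counted. The patterns with every injection at Grade ≥ 3 show the logic of the rule and are not a forecast.

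This is most likely a drafting slip. It should be corrected because it sits in a decision threshold of a first-in-human trial.

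**What to change.** Amend 9.3.3.3 so that all three percentage rules read Grade ≥ 3 in both the entry clause and the persistence clause. The separate Grade 4 threshold for redness can stay if it is intended.

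The change is a few words. Its cost is a somewhat higher chance of a hold: under the low-rate assumptions above, from 0.002 to between 0.004 and 0.026 for one rule in 12 injections. Any added hold would come from events at least as severe as those the rules already count.

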9.3.3.4 Study Termination

The PI or sponsor may terminate the trial at any time. In the case of study termination, investigators will be informed of the procedures to be followed to ensure adequate consideration is given to the protection of the subject's safety.

[figure not shown]
The Investigator will be responsible for informing the sponsor of the trial's termination within 24 hours. The sponsor has to inform the competent authorities and the ethics committee within 15 days.

9.4 Treatments

9.4.1 Treatments Administered

All eligible subjects will be allocated to one of the two dose cohorts according to the assignment list. Each subject will receive two or three vaccine injections administered as i.m. injections in the deltoid region of the upper arm muscle.

For safety reasons dose administration in each dose level will be performed in four groups. Dose administration for the first subject at all dose levels will be vaccinated 48 hours prior to the second groups (second and third subject) of this dose level. The second and the third subject will be vaccinated in an interval of at least 5 min and after a period of at least 48 hours after the first subject to assess for immediate hypersensitivity reaction (within 60 min after the vaccination) or cytokine release (within 24 hours following the vaccination). The next group of four subjects can be vaccinated in parallel (in intervals of at least 5 min) at least 24 hours after the second group and at least 24 hours before the last group. The last group of the dose cohort including five subjects will be dosed on the same day in intervals of at least 5 min. Dosing events are supervised by an Investigator.

Figure 1: Dose administration groups

A Local Safety Board will be established for this study. Planned 2nd immunization and dose escalation will occur following a review of the interim safety report. Interim safety reports will contain safety data obtained until day 7.

The second immunization for each subject will be done after the Local Safety Board reviewed individual safety data of the respective subject.

All subjects who consented to the study extension will be immunized a third time with a vaccine dose of 1×10^8 pfu MVA-MERS-S at 12 months (± 4 months) after the first vaccination.

For the decision about dose escalation safety data obtained until day 7 after the second immunization of all subjects of the first cohort will be taken into account.

A dose level may be repeated and furthermore, additional dose step(s) may be added but not exceeding dose of 1×10^8 pfu MVA-MERS. The decision to repeat and/or to modify the dose level and/or to add additional dose steps will be taken by the Local Safety Board and the Ethics Committee and Competent Authority will be notified.

Repetition or modification of dose steps are only assumed for the second cohort if dose escalation is not possible due to safety-events observed within the lower dose cohort. Safety-events may be observed within the lower dose cohort that do not lead to study termination according to the holding rules but also do not warrant the increase of the dose up to 1×10^8 pfu MVA-MERS. In this case, the second cohort may be vaccinated with the same dose as the first cohort or a dose lower than 1×10^7 pfu MVA-MERS may be applied.

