7.4.1.4 Summary of Potential Risks for Study Participants

In summary, preclinical data suggest a favorable safety and tolerability profile. An extensive body of relevant preclinical studies have been conducted that are needed to proceed to Phase I clinical testing. Although potential risks are known, such as Myo-/pericarditis, Vaccinia rash, eczema vaccinatum, Post-vaccinial encephalitis, so far clinical trials on MVA have reported transient and spontaneously resolved adverse events and no serious ones. Based on available information and the design of the study, the sponsor and the PI consider the trial to be ethically acceptable. The duration of confinement, the medical surveillance and the chosen time intervals for the sequential dosing of the first, second and third subjects of each dosing cohort are considered adequate to ensure maximal safety of the subjects and have been established with guidance of the competent authority. Thus, taking into account the safety measures to minimize risks for study participants, the exposure of healthy subjects with MVA-MERS-S vaccine is justified since the potential risks and disadvantages for study participants are outweighed by the potential benefits for medical research, medical practice and eventually for individuals at risk of MERS.

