9.4.10.3.4 Ambulatory Visits

Subjects will return to the study ward for ambulatory visits on study day 3, 7 and 14 (± 2), after the first vaccination and on study day 35, 42 (± 2), 56 (± 3), 84 (± 3) after the second vaccination. On the ambulatory visits the following events will be performed:

- Targeted Physical Examination (only on day 42)
- Vital signs/ Temperature
- 12-lead ECG (only on day 7, 14, 35, 42)
- Injection Site reaction & systemic events/ reaction assessment (only on day 3, 7, 14, 35 and 42)
- Safety Laboratory (Urine) (only on day 7, 14, 35, 42)
- Safety Laboratory (Blood) (only on day 3, 7, 14, 35, 42)
- Blood sampling for troponin (only on day 7, 14, 35, 42)
- Blood sampling for humoral immunogenicity (only on day 7, 14, 35, 42, 56, 84)
- Blood sampling for cellular response (only on day 14, 42, 56, 84)
- PBMC freezing and plasma aliquots
- Blood sampling for RNA storage (only on day 3, 7, 35)
- Blood sampling for innate immunity (only on day 3, 7, 35)
- Adverse events assessment
- Concomitant medication assessment
- Collection and review of diary

9.4.10.3.5 Ambulatory vaccination and subsequent ambulatory visits (only for subjects who gave consent to the study extension)

Subjects will return to the study ward for an ambulatory vaccination visit 12 months (± 4 months) after the first immunization.

The following interventions will be performed:

- Informed Consent
- I/E Criteria check
- Update medical history
- Weight
- Physical examination
- Vital signs / Temperature
- 12-lead ECG
- Injection Site reaction & systemic events/reaction assessment
- AE/ConMed
- Alcohol Breath Test
- Urine Drug Screen
- Urine Pregnancy Test
- Safety Laboratory (Urine/Blood)
- Blood sampling for humoral immunogenicity
- Blood sampling for cellular response
- PBMC freezing and plasma aliquots
- Blood sampling for RNA storage
- Blood sampling for troponin
- Blood sampling for innate immunity
- Dosing
- Training on subject diary

After dosing the following events will be performed **at 2 h, 4 h and 6 h**:

- Vital signs (and at 0 h, before dose administration)
- Temperature (and at 0 h, before dose administration)
- (AE)/ConMed (and at 0 h, before dose administration)
- Injection site reactions & systemic events/reactions assessment

Subjects will return to the study ward for ambulatory visits on study day 1, 3, 7 and 14 (± 2), after the third vaccination.

On the ambulatory visits the following events will be performed:

- Vital signs/ Temperature

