9.6.4 Data Management

Data management will double check all eCRF entries as defined in the DMP. Quality control and data validation procedures such as programmed automatic edit and consistency checks ensure data validity and accuracy immediately at the point of entry into the clinical database. The database application which is used to capture electronic study data is fully CFR part 11 compliant. Thus, it is access restricted, demands electronic signatures, maintains an electronic audit trail and provides appropriate backup functionalities. Details of the application and eCRF configuration and all further data management procedures will be described in the data management plan (DMP).

The database will only be locked after all queries and discrepancies that may occur during data entry are resolved.

Upon request safety reports and interim analysis will be generated and provided to the respective members of the Local Safety Board.

After database lock, the data in the study data base will be exported and SAS datasets will be compiled for statistical analysis. The data will be exported in SAS transport files or other SAS-compatible format and transferred electronically to the responsible biometrician for statistical analysis. The locked SAS database will be used to generate the subject listings, tabulations, and analyses.

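### Section 9.4.1 cuts interim safety reports at day 7, so the cohort report before the second immunization omits, on its plain reading, the day 14 ECG, troponin T and laboratory results

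*Protocol*

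**What the plan says.** Protocol section 9.4.1 says that the second immunization and the dose escalation each follow a review of the interim safety report. The next sentence sets its content: "Interim safety reports will contain safety data obtained until day 7". For escalation, the same section separately fixes the cut at day 7 after the second immunization of all cohort 1 subjects.

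The Synopsis and section 9.10 require a report covering adverse events, vital signs, ECGs and safety laboratory data, which "will be prepared and reviewed by the Principal Investigator and Medical Monitor before the second immunization for each dose cohort". Neither gives a data cut, so 9.4.1 is the only place that does.

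A second review before dose 2 is made subject by subject: "The second immunization for each subject will be done after the Local Safety Board reviewed individual safety data of the respective subject". It carries no day limit.

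The relevant measurements appear in Table 1a and in section 9.4.10.3.4: "12-lead ECG (only on day 7, 14, 35, 42" and "Blood sampling for troponin (only on day 7, 14, 35, 42". Blood and urine safety laboratory tests are also scheduled on day 14. Section 7.4.1.4 explains why the cardiac readings are taken into account here: "Although potential risks are known, such as Myo-/pericarditis".

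**The concern.** Dose 2 is given on day 28, three weeks after the stated cut. Between the two lies a full safety visit on day 14 with ECG, troponin T, and blood and urine laboratory tests. If the cohort report stops at day 7, the document that shows all 12 subjects side by side before re-dosing contains a single post-dose ECG and a single post-dose troponin T value per subject.

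At stake is a pattern across subjects, such as modest troponin or ECG shifts in two or three of the 12 that first show at day 14. Such a pattern is easiest to see in a cohort table and harder to see in separate files. Because dosing is staggered, the first subject's individual review does not require the Board to look at the other eleven subjects' day 14 results.

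**Working it through.** The plan gives no sample-size or power figure on this point. The check is a count of scheduled assessments and a calendar.

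**Inputs**
- Report cut: day 7 (9.4.1). Dose 2: day 28 (Synopsis, 9.1); Table 1a shows no window for it.
- Assessments after dose 1 and before day 28 (Table 1a, 9.4.10.3.4): ECG on days 7 and 14; troponin T on days 7 and 14; blood laboratory on days 1, 3, 7, 14 and 27; urine laboratory on days 7, 14 and 27. The day 14 window is ±2 days.
- Day 28 ECG and troponin T are not counted, because the schedule does not say whether they precede dose 2.
- Stagger within a cohort (9.4.1): groups of 1, 2, 4 and 5 subjects, at least 48 h, 24 h and 24 h apart.

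**What a day 7 cut leaves out**

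| Assessment | In the report | Left out |
|---|---|---|
| ECG | 7 | 14 |
| Troponin T | 7 | 14 |
| Blood laboratory | 1, 3, 7 | 14, 27 |
| Urine laboratory | 7 | 14, 27 |

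For ECG, and likewise for troponin T: 12 subjects × 1 omitted time point = 12, out of 12 × 2 = 24, or 50%. The loss is smaller for blood laboratory tests, where the report holds 3 of the 4 time points through day 14. Day 27 is too close to dosing for any report, so day 14 is the avoidable omission.

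**Is day 14 obtainable in time?** Let L be the days between the first and last dosing group of a cohort.
- Minimum L = 48 + 24 + 24 = 96 h = 4 days, covering 1 + 2 + 4 + 5 = 12 subjects.
- Latest day 14 visit of the last group: L + 14 + 2 = L + 16. Margin to the first dose 2: 28 − (L + 16) = 12 − L.
- Day 7 visit of the last group: L + 7. Margin: 28 − (L + 7) = 21 − L.

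| L (days) | Margin, full day 14 report | Margin, day 7 report |
|---|---|---|
| 4 | 8 | 17 |
| 7 | 5 | 14 |
| 12 | 0 | 9 |
| 14 | −2 | 7 |
| 21 | −9 | 0 |

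At L = 4 the last day 14 visit falls by calendar day 20, 8 days before the first dose 2. The protocol sets no maximum for L, so values above 4 are assumptions that show the range.

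**Alternative reading of the cut.** Day 7 might mean the calendar date on which the last group reaches its own day 7. At L = 4 that is calendar day 11. The first subject's day 14 window opens on day 12, so the report still holds no day 14 visit. From L = 5 (5 + 7 = 12) some early subjects' day 14 visits could fall inside the cut.

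**Would the holding rules catch it?** Under 9.3.3.3 the unsolicited rule needs more than 25% of subjects. With the 12 of one cohort as denominator, 3/12 is exactly 25%, so 4 are needed, each with a persistent event of Grade 3 or higher judged probably or definitely related. A milder shift in two or three subjects would not trigger it.

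**The case against.** A reader might infer that day 14 data are barred from review before dose 2, and that a safeguard in a first-in-human trial is missing. The documents do not support that.
- The individual review has no day limit and applies to all 12 subjects. The Board is small (medical monitor, Principal Investigator or deputy, sponsor representative) and includes the intended readers of the cohort report. Each subject's own day 14 results can therefore be considered before that subject's dose 2.
- The holding rules run throughout the study, and a single serious event that may be related to the vaccine is enough to activate them.
- Section 9.10 provides that "a Local Safety Board meeting will be conducted whenever safety relevant data occur that might have an influence on the trial".
- Section 9.6.4 adds: "Upon request safety reports and interim analysis will be generated and provided to the respective members of the Local Safety Board".

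The sentence also does not say that later data are excluded, so it can be read as a minimum. It is still the only stated rule for the report's content, and nothing in it asks for more than day 7.

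A reader might also make something of the sentence not naming the immunization. That is harmless: before dose 2 there has been only one, and the escalation cut is spelled out separately.

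Day 7 is a workable choice as well. The solicited holding rules need onset within 3 days and persistence for up to 72 h, which day 7 generally covers. The 8-day margin must absorb data entry, full source verification and the review itself. Nothing in the protocol says that cardiac signals first appear at day 14.

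Most of this stands, and it makes the point minor. It does not remove it: the individual review covers only the respective subject, ad hoc meetings depend on someone recognising a signal, and on-request reports depend on a request.

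**Conclusion.** The point holds as a minor improvement. On its plain reading, 9.4.1 leaves the day 14 ECG, troponin T and laboratory results out of the only cohort-level report required before dose 2. That is 12 of 24 post-dose-1 readings each for ECG and troponin T per cohort, although at the minimum stagger the visits are complete 8 days before the first dose 2. What may be missing is a cohort view of these data, while the data themselves and a route to the Board remain in place.

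This rests on two assumptions: that the sentence is applied as a cut-off, and that cohort dosing spreads over no more than about 12 days, beyond which a full day 14 report before the first dose 2 cannot be assured.

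**What to change.** In section 9.4.1, replace the sentence on report content with wording such as: *The interim safety report before the second immunization will contain safety data at least until day 7 after the first immunization for all subjects of the cohort, plus all further safety data available at the time of the review, including day 14 ECG, troponin T and laboratory results.* The separate sentence on the escalation decision stays as it is.

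The change needs no new visit, sample or stopping rule. Its cost is a slightly later data cut and less time for data cleaning before the review. Only the day 7 data stay mandatory, so day 14 results are not a precondition and dose 2 is not delayed if dosing spreads out. For the same reason, a report can still comply without day 14 results when they are not yet available.
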